12.2 Study oversight

Primary data collection based on source-documented hospital chart reviews will be performed by the Valtech personnel or its designee monitor at each clinical site. Electronic case report forms will be completed in an expedited fashion.

Each site will be visited regularly to ensure that the study is conducted in full compliance with all applicable regulations and the investigational plan. A pre-study meeting will be held with each potential investigational site in order to inform the prospective investigator and staff concerning features of the investigational device, investigation plan, applicable regulations and requirements, and expectations of the study, including the number and time frame for subject enrolment, subject selection, informed consent, required clinical data and record keeping.

The prospective investigational site will be evaluated to ensure that it has an adequate subject base and can provide sufficient staff and documentation support to conduct the study properly.

The Valtech study monitor will maintain personal contacts with the investigator and staff throughout the study by telephone, mail, e-mail, and on-site visits. The monitor will compile and file an observation report at each visit. Monitoring is intended to ensure continued protocol compliance, adequate subject enrolment, accurate data reporting, and adequate accounting of the investigational device.

	TRI-REPAIR – Tricuspid Regurgitation RePAIR with CaRdioband Transcatheter System (TR1-1). Study protocol	[REDACTED] [REDACTED] [REDACTED]
---	---	--

Upon closure of the study at an investigational site, the study monitor will make a final onsite visit. The purpose of this visit is to collect all outstanding study documents, ensure that the investigator's files are accurate and complete, review record retention requirements with the investigator, make a final accounting of all study supplies shipped to the investigator, provide for appropriate disposition of any remaining supplies, and ensure that all applicable requirements for the study are met. The observations and actions made at this visit will be documented as a final report for investigators and Valtech's acceptance.

12.3 Data management

The sponsor agrees to be responsible of the verification that the trial is conducted implementing and maintaining quality assurance and quality control systems with written SOPs to ensure that the trials are conducted and data are generated, documented (recorded), and reported in compliance with the protocol, GCP, and the applicable federal, state and local laws, rules and regulations and guidelines relating to the conduct of the clinical trial.

12.4 Data collection and review

The investigator, or an individual designated by the investigator, is responsible for recording all data from the trial on the eCRF's supplied by Valtech.

Valtech personnel or its designee will review completed eCRF's at the investigational site at regular intervals throughout the investigation. To this end, the investigator must permit inspection of the investigation files and subject CRF's by such representatives and/or responsible governmental agencies.

All eCRF's will be tracked at Valtech and missing or unclear data will be requested as necessary throughout the investigation. Valtech or the monitor will request additional documentation, such as physician and/or laboratory procedure notes, in the event that complications or malfunctions are observed and reported.

12.5 Data capture

An Electronic Data Capture (EDC) system will be used for this study (EDC2go by Genae, a CRO and Data company based in Belgium and in the US). EDC2go is a software based CRF, designed to be FDA 21 CFR Part 11 compliant to collect data electronically. The system allows validation of data in terms of completeness accuracy. Each deviation from required fields, such as missing data, out of range data, or inappropriate data, will generate an automatic query, for the site to address.

The system is compliant with FDA 21 CFR Part 11; meaning it is secured, and users are obliged to have their own password-protected username. Each data entry is registered and a complete audit trail is available at all times.

A query will be generated when:

1. A validation rule is not followed – generated automatically by the EDC system, or

	TRI-REPAIR – Tricuspid Regurgitation RePAIR with CaRdioband Transcatheter System (TR1-1). Study protocol	[REDACTED] [REDACTED] [REDACTED]
---	---	--

2. During a monitoring visit, when there is inconsistency with the source documents - Manually by the monitor.

The queries will remain open in the EDC system, until the designated site staff answer the question. The monitor will then be alerted of a new available answer, and only following re-monitoring, if the answer is sufficient, the query will be closed.

Upon study completion, all data will be collected, and all queries will be answered, the data will be extracted and forwarded to an expert statistician for analysis. The data collected will be incorporated into the final report of this clinical study.

13 SPONSOR DUTIES AND RESPONSIBILITIES

13.1 Role of the Sponsor

As the sponsor of this clinical study, Valtech has the overall responsibility for the conduct of the investigation. Valtech will have certain direct responsibilities and will delegate other responsibilities.

The general duties of Valtech consist in submitting the clinical investigation notification to National Competent Authorities, obtaining Ethics Committee approvals prior to patient's enrollment, selecting qualified investigators, ensuring proper investigational site monitoring, and ensuring that informed consent is obtained. Valtech will prepare written progress reports and a final report, as required.

Valtech will select qualified investigators; ship devices only to qualified participating investigators, obtain a signed Investigator's Agreement, and provide the investigators with the information necessary to conduct the study.

Valtech or its designees will conduct investigational site monitoring to ensure that all investigators are in compliance with the investigational plan and the Investigator's Agreement. The monitors will verify source documentation against completed eCRF's and resolve any discrepancies. Monitors and Valtech will evaluate circumstances where an investigator deviates from the investigational plan. Valtech retains the right to remove either the investigator or the investigational site from the study.

13.2 Study suspension or termination procedures

Valtech reserves the right to terminate this study and remove all study materials from the study site at any time. The study may be suspended or terminated for any of the following reasons:

- It becomes apparent that subject enrolment is unsatisfactory with respect to quality or quantity
- Data recording is inaccurate and/or incomplete
- Violation or deviations from the signed protocol
- The incidence and/or severity of adverse events in this or in other studies indicate a potential health hazard caused by the treatment under study.

Should a determination be made that the study should be suspended or terminated at one or all sites, then:

	TRI-REPAIR – Tricuspid Regurgitation RePAIR with CaRdioband Transcatheter System (TR1-1). Study protocol	[REDACTED] [REDACTED] [REDACTED]
---	---	--

1. Enrolment shall be suspended or terminated at one or all the sites
2. Currently enrolled subjects will be followed according to the protocol, which may be amended to accommodate study suspension or termination
3. Valtech shall promptly inform the investigators and Ethics Committees of the suspension or termination and the reasons for it.

Should Valtech decide to terminate the study, the investigator will complete the eCRFs as far as possible. The completed eCRFs and any study materials will then be collected by Valtech.

13.3 Sponsor study files

Valtech will maintain copies of correspondence, data, shipment of devices, adverse device effects and other records related to the investigational plan. Valtech will maintain records related to the signed Investigator's Agreements.

	TRI-REPAIR – Tricuspid Regurgitation RePAIR with CaRdioband Transcatheter System (TR1-1). Study protocol	[REDACTED] [REDACTED] [REDACTED]
---	---	--

1 SYNOPSIS OF STUDY DESIGN AND PROCEDURES

1.1 Purpose of the statistical analysis plan (SAP)

The SAP (methodology) provides detailed description of the planned analyses and methodology for Study TR1-1 (TRI-REPAIR – Tricuspid Regurgitation (TR) Repair with Cardioband Transcatheter System). This SAP is based on the study protocol for TR1-1 Rev 05, dated May 25, 2017.

1.2 Study objectives

The objectives of this early feasibility study are to assess the safety and technical success of the Cardioband system for the procedure of symptomatic chronic functional tricuspid regurgitation.

1.3 Study design

This clinical investigation is a single arm, multi-center, prospective study with intra-subject comparisons. Candidates for Cardioband TR procedure are symptomatic subjects with functional tricuspid valve repair. Subjects are selected upon clinical conditions and severity of TR. Anatomical feasibility is assessed by Echocardiography and/or other exams (such as computerized tomography and angiography) according to the site common practice. Subjects will be screened and enrolled according to the study inclusion and exclusion criteria.

Subjects will undergo tricuspid valve repair with Cardioband implanted via transcatheter procedure under Transoesophageal/Intracardiac echocardiography (TEE/ICE) and fluoroscopy guidance. Post-procedure clinical care will be performed according to standard management of valve repair; Clinical follow-up including standard post-procedural management of surgical valve repair and Transthoracic Echo (TTE) assessment of the degree of Tricuspid regurgitation will be obtained at hospital discharge, 30 days, 6, 12 and 24 months post-index procedure.

As the follow up at 30 days is of most importance in terms of the subject's safety, the first 3 subjects will have to complete 30 days follow up before the recruitment of additional subjects. In relation to the first 3 subjects, recruitment will continue in case of elongated hospitalization or complications that are unrelated to the study device as will be judge by the study clinical event committee.

1.4 Sample size

A sample size of up to 60 patients is considered adequate to further confirm the safety and performance of the Cardioband System in TR patients. Considerable clinical data on the safety of clinically equivalent devices exists. This will enable a comparison of clinical data obtained in this study with literature data from prior studies.

1.5 Sample Size Justification

Reference values for calculations are based on a literature review of predicate devices and clinical experience in previous Valtech adjustable and mitral annuloplasty devices. A sample size of 60 subjects allows accurate estimates of risk associated the device (even for rare events). The sample size was selected through the width of the two-sided 95% exact confidence interval of the potential adverse event rates.

2 STUDY ENDPOINTS

2.1 Primary endpoints

Safety

Primary safety endpoints will be measured at hospital discharge and 30 days post-procedure.

1. Major serious adverse events (MSAEs)

- Death
- Myocardial infarction
- Cardiac tamponade
- Device related cardiac surgery
- Stroke

Technical success

Primary technical success endpoints will be measured throughout the procedure and at discharge.

1. Successful Cardioband procedure
2. Cardioband completely implanted
3. Any reduction in septolateral diameter

2.2 Secondary endpoints*

Secondary endpoints will be measured at baseline, discharge, 1, 6, 12, and 24 months post procedure.

1. Tricuspid regurgitation
2. Effective regurgitant orifice area (EROA)
3. Regurgitant volume
4. Tricuspid annular plane systolic excursion (TAPSE)
5. New York Heart Association (NYHA) Class
6. Six Minute Walk Test (SMWT)
7. Kansas City Cardiomyopathy Questionnaire (KCCQ)
8. Left ventricular ejection fraction (LVEF)
9. N terminal pro B type natriuretic peptide (NT-pro BNP)
10. GOT aka aspartate aminotransferase (AST), GPT aka alanine transaminase (ALT), bilirubin
11. Blood urea nitrogen (BUN) creatinine clearance
12. Diuretic therapy

**Note. Although originally included in the protocol, secondary endpoints:*

- (a) Left ventricular end diastolic volume index (LVEDVI)*
- (b) Left ventricular end systolic volume index (LVESVI)*
- (c) Activity by wearable device*

will not be analyzed due to their limited relevance to main study objectives

Table 2. Summary of primary and secondary endpoints

Endpoint	Baseline	Discharge	1 Month	6 Months	12 Months	24 Months
MSAE		x	x			
Technical success		x				
Tricuspid regurgitation	x	x	x	x	x	x
EROA	x	x	x	x	x	x
Regurgitant volume	x	x	x	x	x	x
TAPSE	x	x	x	x	x	x
NYHA	x	x	x	x	x	x
SMWT	x	x	x	x	x	x
KCCQ	x	x	x	x	x	x
LVEF	x	x	x	x	x	x
NT-pro BNP	x	x	x	x	x	x
AST	x	x	x	x	x	x
ALT	x	x	x	x	x	x
Bilirubin	x	x	x	x	x	x
BUN	x	x	x	x	x	x
Diuretic therapy	x	x	x	x	x	x

2.3 Analysis populations

Two analysis cohorts will be defined as below:

- Intent-to-treat (ITT) cohort includes all subjects who signed informed consent, met eligibility criteria, and for whom the study procedure has been attempted.
- As-treated cohort is a subject of the ITT cohort and includes all subjects for whom the study device is implanted and remains in the position at the time of the subject's exit from the procedure room.

The primary safety analysis will be performed on both cohorts with due consideration given to the required follow-up intervals for each cohort. All other analyses will be performed on the as-treated cohort.

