5.5.3 Analysis of performance and safety endpoints

The performance and safety endpoints of the Cardioband System will be assessed by recording the echocardiographic parameters and by monitoring the patient clinical status. Safety assessments will consist of recording of all adverse events, and regular monitoring of haematology and blood chemistry parameters, and vital signs. These parameters are evaluated during the patients' follow-up visits.

Study results will be presented in tabular format. Two sided 95% exact confidence intervals will be presented where required. Continuous variables will be summarized by a mean, standard

	TRI-REPAIR – Tricuspid Regurgitation RePAIR with Cardioband Transcatheter System (TR1-1). Study protocol	
---	---	---

deviation, minimum, median and maximum. Categorical variables will be summarized by a count and percentage. If statistical tests will be done the significance level will be equal to or lower than 5%. Nominal p-values will be presented. Where confidence limits are appropriate, the confidence level will be 95%.

Baseline demographic and other baseline characteristics, together with safety analyses will be performed on all subjects.

The numbers of subjects who entered and completed each visit of the study will be provided, as well as the reasons for all discontinuations, grouped by major reason (e.g., lost to follow-up, adverse event, etc.). A list of discontinued subjects, protocol deviations, and subjects excluded from the efficacy analysis will be provided.

Descriptive statistics will be provided for the efficacy and safety outcome results.

The analysis of all adverse events will include incidence tables and incidence tables by severity, relationship to treatment and baseline parameters. Serious adverse events will be listed and discussed individually.

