6.6 Screening failure

A screening failure will be defined as patient who fulfilled the theoretical eligibility criteria, and was intended to treat, however Cardioband was not be implanted due to new information detected at the time of procedure, preventing the implantation. A screening failure will be followed until discharge from hospital.

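### SAP 2.3 makes eligibility a condition of the ITT cohort; read literally, a subject treated despite an eligibility violation is missing from the primary safety rate, which the protocol bases on all subjects

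*SAP*

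**What the plan says.** SAP 2.3 opens with "Two analysis cohorts will be defined as below". The first is ITT: "Intent-to-treat (ITT) cohort includes all subjects who signed informed consent, met eligibility criteria, and for whom the study procedure has been attempted". The second is drawn from it: "As-treated cohort is a subject of the ITT cohort", where the word subject is evidently a slip for subset.

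The cohorts are then assigned to analyses. For safety: "The primary safety analysis will be performed on both cohorts with due consideration given to the required follow-up intervals for each cohort". For the rest: "All other analyses will be performed on the as-treated cohort".

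Protocol 5.5.3 sets the population differently: "Baseline demographic and other baseline characteristics, together with safety analyses will be performed on all subjects". The only exclusions it mentions concern efficacy: "A list of discontinued subjects, protocol deviations, and subjects excluded from the efficacy analysis will be provided".

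**The concern.** An ITT or safety population normally holds everyone exposed to the intervention. Here membership also depends on having satisfied the entry criteria, and no safety population or all-attempted population catches those who did not.

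Death, stroke, tamponade and the other MSAE components occur during or after the procedure. If eligibility is settled or revisited after that point, the denominator and numerator of a primary endpoint can depend on decisions taken with outcomes in view. The study is open and has one arm, so blinding gives no protection. Protocol 5.5.1 and 5.5.2 intend the rates to be compared with literature and historical data, so a rate that leaves out some exposed subjects would not describe the treated population in that comparison.

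**Working it through.** **Step 1: follow one subject through the definitions.** Take a subject who consented, underwent an attempted procedure, and did not satisfy one entry criterion.

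- ITT (SAP 2.3) needs consent, eligibility and an attempt. The second condition fails, so the subject is not in ITT.
- As-treated is contained in ITT, so the subject is not in as-treated, even with a device in place.
- Primary safety uses these two cohorts, so the subject is not in the MSAE rate.
- Everything else uses as-treated, so the subject is also absent from the technical success, echocardiographic and clinical analyses and from the adverse event tables of SAP 4.5.
- SAP 4.7 (protocol deviations) might show the violation, but a listing does not put the subject into a rate.

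**Step 2: compare with the protocol.** Section 5.5.3 attaches no eligibility condition to its safety population. The SAP says in 1.1 that it is based on the protocol. Where it drops protocol content elsewhere (LVEDVI, LVESVI and wearable activity, in the note to 2.2), it says so and gives a reason. For the narrower safety population it gives neither.

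**Step 3: size.** The documents state no figure tied to this point and no expected number of violators, and the rates and widths behind the sample size are redacted. There is therefore nothing to reproduce. What follows is an illustration with assumed counts.

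Inputs: n = 60 subjects attempted (the planned maximum, protocol 5.5.1 and SAP 1.4); x = 3, 6 or 9 subjects with an MSAE (assumed); k = 1 violator dropped, with e = 0 or 1 event (assumed).

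Rate after dropping = (x − e)/(n − k). It falls only if e/k exceeds x/n, that is, if violators have a higher event rate than the whole group. The 95% intervals are Clopper-Pearson, as in SAP 3.1. For r events in m subjects, the lower limit is the 2.5% quantile of Beta(r, m − r + 1) and the upper limit is the 97.5% quantile of Beta(r + 1, m − r).

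| All 60 kept | One violator with an event dropped | One violator without an event dropped |
|---|---|---|
| 3/60 = 5.0% (1.0–13.9) | 2/59 = 3.4% (0.4–11.7) | 3/59 = 5.1% (1.1–14.1) |
| 6/60 = 10.0% (3.8–20.5) | 5/59 = 8.5% (2.8–18.7) | 6/59 = 10.2% (3.8–20.8) |
| 9/60 = 15.0% (7.1–26.6) | 8/59 = 13.6% (6.0–25.0) | 9/59 = 15.3% (7.2–27.0) |

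Dropping one violator with an event lowers the rate by 1.4 to 1.6 percentage points (for example 10.0 − 8.5 = 1.5). Dropping one without an event raises it by 0.1 to 0.3 points. The intervals overlap heavily in every row.

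**The case against.** The strongest reply is that the three ITT conditions may simply describe the enrolment sequence: consented, accepted, taken to the procedure. Protocol section 7 sets up a central eligibility committee with the final say on enrolment. On that reading, an accepted and treated subject stays in ITT whatever is found later, and nothing in the SAP says that eligibility is re-judged. This is a fair reading, and it means that exclusion of violators is a consequence of the literal wording, not a documented intention. It does not settle the matter, because the SAP does not say which meaning applies. If acceptance is meant, the condition adds almost nothing and can go; if later review is meant, it does harm.

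It can also be said that the protocol does not define all subjects, and that its sections 6.1 and 6.2 allow only eligible patients to take part. That softens the conflict, but those sections govern who should be enrolled. They do not say how to analyse someone who was treated in error.

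The events would not disappear either. The CEC reviews all SAEs (protocol 10.7), SAEs are to be discussed individually and deviations listed (5.5.3), and the stopping criteria (5.4) are not tied to SAP cohorts. This limits concealment but does not restore an MSAE rate.

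A reader might infer three stronger claims that the documents do not support:

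- *Core-lab readings will overturn eligibility.* SAP 2.2 and 3.3 do provide for baseline core-lab values of TR and LVEF, but no visible text uses them to revise eligibility. Protocol 6.4 is partly redacted.
- *Protocol 6.6 foresees treated violators.* It describes patients who had satisfied the theoretical criteria and in whom "Cardioband was not be implanted due to new information detected at the time of procedure, preventing the implantation". For them the question is whether the procedure counts as attempted, which is a different matter.
- *The bias is downward.* Some criteria keep out high-risk patients, such as those with severe right ventricular dysfunction. But a violator with an annulus below 40 mm or TR below 2+ plausibly has milder disease, and dropping such subjects could raise the rate.

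**Conclusion.** The point holds as a defect of definition. On its literal wording SAP 2.3 leaves exposed eligibility violators out of the primary safety rate and all other analyses, against protocol 5.5.3, and it leaves open when and by whom eligibility is judged. That creates room for exclusions made after outcomes are known. It does not show that any are planned.

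Neither the direction nor the size of the bias can be derived from the documents, and the figures above rest wholly on assumed counts. SAP 3.1 states that there are no pre-specified hypotheses, and no performance goal is visible, so no pass-or-fail conclusion is shown to change. Should-fix.

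**What to change.** In SAP 2.3, delete the eligibility condition from the ITT definition, so that the cohort consists of all consented subjects in whom the procedure was attempted. The primary safety rate then covers every such subject. Because as-treated is nested in ITT, the condition also drops out of that cohort. Report eligibility violations in the protocol deviation output (SAP 4.7). If an eligible-only result is wanted, show it as a labelled sensitivity analysis and state there how and when eligibility was determined.

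The cost is three deleted words and at most one extra table row. The downside is that the reported rate may become slightly less favourable. The change helps under either reading of the present wording, because it removes the need to choose between them.
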